10.3 ADVERSE EVENTS FOR THE ANALYSIS OF THE PRIMARY AND SECONDARY ENDPOINTS

10.3.1 Adverse Events for the Analysis of Primary Endpoints 1 and 2

If any of the following invasive actions occur in order to resolve an above listed Protego lead-related AE, the AE will be included in the primary safety endpoint analysis:

- Lead surgically repositioned
- Lead surgically explanted
- Lead surgically replaced
- Lead surgically abandoned
- Other lead-related surgery performed

Additionally, if any of the following non-invasive actions occur in order to resolve an above listed Protego lead-related AE, the Protego lead-related AE will be included in the primary endpoint analysis:

- Lead pacing polarity or pacing mode reprogrammed due to suspected lead failure.
- Lead abandoned and pacing disabled due to clinical failure or suspected lead failure
- Lead use continued based on medical judgment despite a known clinical failure or suspected lead failure

AEs that are corrected by reprogramming the pulse generator (other than the above) and resolved without invasive action will not be considered an adverse event counted towards the primary endpoints. For example, electrical reprogramming of the pacing polarity to eliminate extra-cardiac stimulation will not be considered an adverse event. Similarly, increasing pacing output as a result of an elevated threshold without further intervention does not count toward the primary endpoint analysis.

Subject deaths as a result of a Protego lead-related AE will be included in the primary endpoint analysis.

Primary endpoints 1 and 2 will exclude 1) lead dislodgements that occur within 30 days after lead implant or a lead revision procedure and 2) high pacing threshold, intermittent capture, no lead capture within 30 days after lead implant or a lead revision procedure. However, these will count towards the adverse event secondary endpoint.

In addition, the following two pulse generator-related adverse events will be included in the analysis of primary endpoints 1 and 2: DF4 header connector malfunction and DF4 header fluid intrusion.

10.3.2 Adverse Events for the Analysis of Secondary Endpoint 3

If any of the following invasive actions occur in order to resolve an above listed RA or LV lead-related AE, the AE will be included in the secondary endpoint analysis:

- Lead surgically repositioned
- Lead surgically explanted
- Lead surgically replaced
- Lead surgically abandoned
- Other lead-related surgery performed

Additionally, if any of the following non-invasive actions occur in order to resolve an above listed RA or LV lead-related AE, the AE will be included in the secondary endpoint analysis:

- Lead pacing polarity or pacing mode reprogrammed due to suspected lead failure.
- Lead abandoned and pacing disabled due to clinical failure or suspected lead failure
- Lead use continued based on medical judgment despite a known clinical failure or suspected lead failure

All Implant Procedure-related adverse events are included in secondary endpoint analysis, as well as Pulse Generator-related and Non-Procedure Non-System-related adverse events that require invasive intervention to resolve.

Adverse events excluded from the primary endpoint, as listed in Section 10.3.1, are also included in this secondary endpoint analysis.

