Purpose:	To confirm long-term safety and reliability of BIOTRONIK's Protego DF4 lead, as used in conjunction with a BIOTRONIK DF4 compatible implantable cardioverter defibrillator (ICD) or cardiac resynchronization therapy defibrillator (CRT-D) pulse generator. The evaluation of safety will be based on the analysis of Protego lead related adverse events. The Protego DF4 registry will provide data to permit characterization of any Protego lead failures contributing to loss of bradycardia or shock therapy. Additionally, acute and chronic Protego lead parameters will be evaluated.
Subject Population:	Subjects who are indicated for an ICD or a CRT-D. Subjects must be successfully implanted with a BIOTRONIK Ilesto DF4 ICD or CRT-D or future market released BIOTRONIK DF4 ICD or CRT-D. Enrollment can be up to 30 days prior to or 30 days after implant with the DF4 system.
Enrollment:	This registry will include 1,694 subjects implanted with the Protego DF4 system. The collection of data will continue for 5 years post-implant for each enrolled subject.
Clinical Sites:	Up to 75 U.S. and International sites.
Primary Endpoints:	
 1. Evaluation of the overall incidence of adverse events (AEs) related to the Protego lead or device header 2. Evaluation of the incidence of each individual type of AE that contributes to Primary Endpoint 1
Secondary Endpoint:	
 1. Pacing threshold, sensing and impedance measurements for the Protego lead through 5 years post-implant 2. Shock impedance for the Protego lead through 5 years post-implant 3. AE rates for AEs excluded from primary safety endpoints 1 and 2, through 5 years post-implant
Clinical Events Committee Chair:	TBD
Sponsor:	BIOTRONIK, Inc. Clinical Studies Department [name]

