2.1.3 Secondary Endpoints

There are no formal tests of hypotheses associated with secondary endpoints 1-3.

1. Pacing threshold, sensing and impedance measurements for the Protego DF4 lead through 5 years post-implant.
2. Shock impedance for the Protego lead through 5 years post-implant.
3. Adverse event rates for protocol defined, CEC adjudicated AEs excluded from primary safety endpoints 1 and 2, through 5 years post-implant.

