2.4.3 Missing Data

All possible steps will be taken to minimize missing data in the registry. This includes but is not limited to monitoring of registry forms for completeness and supporting efforts to track and maintain contact with registry subjects during the follow-up period.

The reasons for any missing data in the registry will be documented. BIOTRONIK will examine both missing-data patterns, which describe which values are observed and which are missing, and the missing-data mechanisms, which concerns the relationship between missingness and the values of variables in the registry data set².

For evaluation of the long-term primary registry endpoints (safety endpoints 1 and 2), only subjects who achieve 5 years of follow-up or have experienced an adverse event prior to 5 years will be included in the final evaluation of the associated hypotheses. The secondary endpoint of other AEs at 5 years, excluded from the primary safety analyses, will be analyzed in similar manner. There will be no imputation for these missing adverse event outcomes.

For purposes of Kaplan-Meier survival analyses, described in Section 2.4.2, all AE data on enrolled subjects will be included with follow-up times censored at the time of withdrawal or last completed follow-up visit representing the time of the last known AE status.

² R.J.A. Little and D.B. Rubin, 2002, *Statistical Analysis with Missing Data*, 2nd edition, Wiley and Sons

Secondary endpoints, which include successful sensing and pacing, pacing thresholds, sensing and impedance measurements will be analyzed in two ways. First, all available results will be summarized by scheduled visit through the 5 years of registry follow-up. Secondly, a last value carried forward (LVCF) will be used to estimate the values at the final 5-year follow-up evaluation for subjects who withdraw prior to 5 years.

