10.1.2 Pulse Generator-Related Adverse Events

An AE will be classified as pulse generator-related if any one of the following occurred:

- DF4 header connector malfunction
- DF4 header fluid intrusion
- Device migration
- Premature battery depletion
- Pulse generator failure
- Skin erosion

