10.2 ENDPOINT ANALYSIS

All protocol defined adverse events included in the primary and secondary endpoint analysis will be adjudicated by the Clinical Events Committee (CEC) (see Section 2.1). The CEC will have the responsibility to adjudicate the classification and category of each reported adverse event as implant procedure, implanted pulse generator, lead, or non-procedure non-system related. For each adverse event, the CEC will indicate whether the adverse event relatedness to the Protego lead is: not related, related, possibly related, or unknown.

In evaluation of the two primary endpoints for the post-approval registry, the estimates of AE rates will be based on the number of subjects with at least one "related" AE as a proportion of total subjects. Subjects with a final adjudicated related AE classification of "possibly related", "not related" or "unknown" will not have that individual event contribute to or be included in the evaluation of primary safety endpoints. The same rules will be used for purposes of Kaplan-Meier survival analyses, described in Section 2.4.2.

Secondary endpoint 3, which includes AEs that were excluded from primary safety endpoint 1 through 5 years post-implant, will also be summarized as AE rates along with their associated, exact 95% confidence intervals.

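### Section 10.3.2 lets a lead-related DF4 header event resolved invasively into secondary endpoint 3 although Section 10.3.1 already counts it in the primary endpoints, contrary to endpoint 3's own definition

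*Combined protocol and SAP*

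**What the plan says.** **Definition of endpoint 3.** Section 2.1.3 defines it as "Adverse event rates for protocol defined, CEC adjudicated AEs excluded from primary safety endpoints 1 and 2, through 5 years post-implant". The Summary has the same content. Section 2.4.3 speaks of "The secondary endpoint of other AEs at 5 years, excluded from the primary safety analyses, will be analyzed in similar manner", and Section 10.2 of "Secondary endpoint 3, which includes AEs that were excluded from primary safety endpoint 1 through 5 years post-implant"; Section 2.4.1 describes it in the same way. All five places treat endpoint 3 as what the primary endpoints leave over.

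**Class of the header events.** Section 10.1.2 opens its list with "An AE will be classified as pulse generator-related if any one of the following occurred". The first two items are malfunction of the DF4 header connector and fluid intrusion into the DF4 header.

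**Primary rule.** Section 10.3.1 says of these items that "the following two pulse generator-related adverse events will be included in the analysis of primary endpoints 1 and 2". It sets no condition on the action taken to resolve them.

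**Relatedness filter.** Section 10.2 bases the primary rates on events the CEC adjudicates as 'related' to the Protego lead. Events adjudicated possibly related, not related or unknown do not count.

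**Secondary rule.** Section 10.3.2 takes in all implant procedure events, "as well as Pulse Generator-related and Non-Procedure Non-System-related adverse events that require invasive intervention to resolve". Its last sentence adds that events excluded from the primary endpoint under Section 10.3.1 are included too.

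**The concern.** The rule in Section 10.3.2 works on the whole pulse generator class, while Section 10.3.1 has already taken two members of that class into the primary endpoints. Nothing in Section 10.3.2 removes them again. A programmer who codes endpoint 3 from that section alone would include events that the definition in Section 2.1.3 keeps out. One who codes from the definition would not. The plan therefore supports two different endpoint 3 counts.

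At stake is a clean report of a small group of events that matter in this registry. Sections 1.3 and 1.4.2 present the connector as the main change from the predecessor lead, and Section 1.4.3 describes a more complex header cavity with strict sealing requirements. It should be clear where a header event is counted, and that it is counted in one place.

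**Working it through.** No alpha, power or sample size enters, and the plan gives no figure for this overlap that could be reproduced. The check is a comparison of rules, followed by one line of arithmetic.

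**Step 1: apply each rule to each kind of header event.**

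| Header event | Primary endpoints (10.2 with 10.3.1) | Generator rule in 10.3.2 | Definition of endpoint 3 | Result |
|---|---|---|---|---|
| Adjudicated 'related', resolved invasively | in | in | out | meets both rules, against the definition |
| Adjudicated 'related', resolved without invasive action | in | out | out | primary only, consistent |
| Not adjudicated 'related', resolved invasively | out | in | in | endpoint 3 only, consistent |

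A header event that is neither adjudicated 'related' nor resolved invasively meets neither inclusion rule, so no overlap arises. The conflict is confined to the first row.

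**Step 2: look for text that removes the first row.** The last sentence of Section 10.3.2 brings in events excluded from the primary endpoint in addition to those already listed. It widens the set and does not narrow the generator rule. No section says that the definition in Section 2.1.3 prevails over the list in Section 10.3.2.

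**Step 3: size per subject.**

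- Let x be the number of subjects with an endpoint 3 event under the definition, N the number evaluable, and k the number of first-row subjects with no other endpoint 3 event.
- Rate under the definition: x/N. Rate under the literal rule, if the k subjects are already in the denominator: (x + k)/N. Difference: k/N.
- Take N = 1000, the evaluable number that Section 2.3 plans for primary endpoint 2. Using it for endpoint 3 is an assumption, based on Section 2.4.3 handling both in a similar way. Then k = 1 gives 1/1000 = 0.1 percentage point, and k = 0 gives 0.
- Section 2.4.3 admits subjects who reach 5 years or have had an event before then. A first-row subject who leaves early could therefore enter the endpoint 3 denominator only because of the header event. For one such subject the difference is (x + 1)/1001 − x/1000 = (1000 − x)/1,001,000, slightly under 0.1 percentage point.

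**Step 4: total size.** This needs k. The documents give no expected rate for either header event, so k cannot be derived.

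**Step 5: effect on the primary endpoints.** The overlap changes only the endpoint 3 count. The events counted for primary endpoints 1 and 2 are the same under either reading, so their tests and the planned 1694 subjects stand.

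**The case against.** The best defence is that the plan already answers the question. Five places describe endpoint 3 as what the primary endpoints exclude. Section 10.3.1 names the two header events individually, whereas Section 10.3.2 mentions generator events only as a class. If the specific rule prevails over the general one, and the list is read within the definition, nothing is counted twice. That is a fair guess at the intent. It remains a guess, because the documents set no order of precedence and Section 10.3.2 is the operational list.

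Several stronger readings are tempting and go too far:

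- *Every surgically treated header event is counted twice.* Section 10.2 keeps events not adjudicated 'related' to the Protego lead out of the primary endpoints, and for those the generator rule correctly points to endpoint 3. Section 10.3.1 does not repeat that condition for header events, but Section 10.2 states it for both primary endpoints. The overlap is certain only for events adjudicated 'related'.
- *The overlap is large, or dominates the generator events in endpoint 3.* There is no header-event rate in the documents to support this, and no separate generator row is specified. A subject may also already count through a procedure event or a right atrial or left ventricular lead event.
- *The overlap is what prevents primary and secondary rates from being added.* No section plans such a sum, and subject-level rates would not add even with disjoint events. In Table 1 for the predecessor leads, 29 + 33 = 62 subjects, yet the combined row shows 60. Event counts there do add, 31 + 34 = 65, so only a similar total of events would be affected.
- *The safety conclusion is at risk.* No header event is lost from the primary endpoints, and Section 2.1.3 attaches no hypothesis test to endpoint 3.

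**Conclusion.** The point holds in a narrow form. As written, Section 10.3.2 admits to endpoint 3 any DF4 header event that is resolved invasively, including those adjudicated 'related' that the primary endpoints already count. For those events the inclusion list contradicts the endpoint's definition.

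The size is about 0.1 percentage point on the endpoint 3 rate for each affected subject with no other endpoint 3 event. This assumes about 1000 evaluable subjects and that Section 10.3.2 is followed literally. The total is unknown and may be zero. The consequence is limited to a descriptive secondary rate and its confidence interval. It is worth correcting because the correction is simple, and its priority is low.

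**What to change.** In Section 10.3.2, after the mention of pulse generator-related events, insert: 'other than DF4 header events (connector malfunction or fluid intrusion) that are counted in primary endpoints 1 and 2'. Tying the exception to events actually counted, and not to the two event types as such, matters: a header event kept out of the primary endpoints, for example because it is not adjudicated 'related' under Section 10.2, then stays in endpoint 3 if it required invasive intervention, and is not dropped from both.

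The cost is one clause and the matching line in the analysis program. No new data, change of sample size or clinical decision is needed.

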4.2 CLINICAL EVENTS COMMITTEE

A Clinical Events Committee (CEC) consisting of at least 3 independent electrophysiologists will be established to review and adjudicate adverse events that occur during the registry. The CEC will be blinded to the clinical registry site and subject identity, and to minimize bias, members will not participate as investigators. The CEC will create a registry specific charter defining the adverse event adjudication process, specifically detailing review guidelines along with appropriate response timelines.

All protocol defined adverse events included in the primary and secondary endpoint analysis (see Section 10.3.1 and Section 10.3.2) will be adjudicated by the Clinical Events Committee. The Clinical Events Committee (CEC) will have the responsibility to adjudicate the classification and category of each reported adverse event. In addition, the CEC will also indicate whether the adverse event is related, possibly related, not related, or has an unknown relation to the Protego lead.

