10.1.4 Non-Procedure Non-System Related Adverse Events

An AE will be classified as non-procedure non-system related if any of the following occur and require a system revision or explant:

- Twiddler's syndrome
- Secondary infection
- Ablation sequelae

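### Section 10.3.2 has no death rule, so a non-procedural RA or LV lead AE that is fatal before any listed action is in neither safety endpoint

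*Combined protocol and SAP*

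**What the plan says.** **Primary endpoints (Section 10.3.1).** A Protego lead-related AE counts if one of five surgical or three non-invasive actions is taken. A separate sentence then adds: "Subject deaths as a result of a Protego lead-related AE will be included in the primary endpoint analysis".

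**Secondary endpoint 3 (Section 10.3.2).** The same two action lists are repeated for the other leads. The surgical route opens "If any of the following invasive actions occur in order to resolve an above listed RA or LV lead-related AE", and the second route "if any of the following non-invasive actions occur in order to resolve an above listed RA or LV lead-related AE". One item on the second list is not an intervention: "Lead use continued based on medical judgment despite a known clinical failure or suspected lead failure". Implant procedure-related AEs all count, "as well as Pulse Generator-related and Non-Procedure Non-System-related adverse events that require invasive intervention to resolve". A last sentence brings in the AEs that Section 10.3.1 lists as excluded from the primary endpoints. There is no sentence on deaths.

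**AE classes.** Under Section 10.1.4 the three listed non-procedure non-system events fall in that class "if any of the following occur and require a system revision or explant".

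**Definition of the endpoint.** Section 2.1.3 defines endpoint 3 as "Adverse event rates for protocol defined, CEC adjudicated AEs excluded from primary safety endpoints 1 and 2", through 5 years. Sections 2.4.1 and 10.2 describe it in the same way, with no mention of an action or intervention.

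**Adjudication.** Section 4.2 states: "All protocol defined adverse events included in the primary and secondary endpoint analysis (see Section 10.3.1 and Section 10.3.2) will be adjudicated" by the CEC. The next sentence makes the CEC responsible for classifying every AE that is reported. Section 10.2 contains the same pair of statements.

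**The concern.** An entry rule based on actions presupposes a subject who lives long enough for the action. Section 10.3.1 deals with this for the Protego lead by naming deaths. Section 10.3.2 borrows the action lists and leaves out the death sentence. An RA or LV lead AE treated by surgery is then counted, while the same AE that kills the subject first is not.

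What is at stake is a reported safety rate that can leave out the worst outcome of the events it describes. A reader of the final report, relying on the definition in Section 2.1.3, would expect these deaths to be in it.

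**Working it through.** **Step 1. Is there a route into either endpoint for a fatal AE with no action taken?**

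| Class of fatal AE | Route | Counted? |
|---|---|---|
| Protego lead-related | Death sentence, 10.3.1 | Yes, primary |
| The two DF4 header types | Named in 10.3.1 with no action required | Yes, primary |
| Implant procedure-related | All included, 10.3.2 | Yes, endpoint 3 |
| RA or LV lead-related, not procedural | Listed action must occur, 10.3.2 | No |
| Other pulse generator | Must *require* invasive intervention, 10.3.2 | Depends on reading |
| Non-procedure non-system | Must *require* revision or explant (10.1.4) and invasive intervention (10.3.2) | Depends on reading |

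**Step 2. Could another clause admit the RA or LV lead death?**

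- *Carry-over sentence.* It reaches only the exclusions listed in 10.3.1: AEs resolved by reprogramming, and dislodgement or capture and threshold problems within 30 days. Those rules concern the Protego lead.
- *Continued use of the lead.* This item needs a known clinical failure or a suspected lead failure. Appendix A defines the first as an inability to sense or pace correctly and the second as a potential mechanical or electrical malfunction. A lead infection or thrombosis (both listed in 10.1.3) is neither.
- *Definition in 2.1.3.* This would admit the death if the CEC adjudicated it, but it conflicts with the operative list in 10.3.2.

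So for RA and LV leads the gap is real on the text of 10.3.2.

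**Step 3. What happens to the denominator?** Section 2.3.1 counts death as loss to follow-up. Section 2.4.3 keeps in the final evaluation only subjects who reach 5 years or have had an AE, and says endpoint 3 is handled similarly, without imputation. If the AE meant there is one that counts for the endpoint, a subject whose fatal AE is not admitted, and who has no other counted AE, leaves numerator and denominator and appears as attrition. If any AE suffices, the subject stays in the denominator as event-free. Either way the death is not in the numerator.

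**Step 4. Size.** The plan's own evaluable number reproduces: 1000/0.9^5 = 1693.5, stated as 1694 enrolled. At 1000 evaluable subjects one event is 1/1000 = 0.1 percentage point. Restoring k deaths to both parts of the fraction gives (x + k)/(1000 + k), which is almost the same: for x = 0 and k = 2, 2/1002 = 0.1996% against 2/1000 = 0.2%.

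The documents give no count of such deaths. If there were 1 to 5 (an assumption), the endpoint 3 rate would be understated by about 0.1 to 0.5 percentage points. Exact (Clopper-Pearson) 95% limits at n = 1000, with assumed counts:

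| Events counted | Deaths restored | Rate | 95% limits |
|---|---|---|---|
| 0 (a single type) | 0 | 0% | 0 to 0.37% |
| 0 (a single type) | 2 | 0.2% | 0.02% to 0.72% |
| 30 (overall) | 0 | 3.0% | 2.03% to 4.26% |
| 30 (overall) | 2 | 3.2% | 2.20% to 4.49% |
| 30 (overall) | 5 | 3.5% | 2.45% to 4.83% |

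**The case against.** The strongest reply is that the gap is narrow and nothing is lost.

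- *Most fatal AEs are covered.* Procedure-related AEs enter without condition, including perforation, primary infection, pneumothorax and pulmonary embolism. Protego lead deaths and the two header types go to the primary endpoints. This stands, and it confines the clear gap to non-procedural RA and LV lead AEs.
- *Generator and non-system AEs.* Section 10.3.2 uses different verbs: RA and LV actions must *occur*, whereas these AEs must *require* intervention. To read *require* as needed rather than received is ordinary usage. This stands, so exclusion of these classes is not established.
- *The data are kept.* Section 3.3.2 requires an AE form for any AE-associated death and a statement on device relation. Section 2.1.4 foresees AEs outside both endpoints and lists them as data of interest. This also stands, but keeping a record is not the same as counting the event in the rate.
- *No decision depends on it.* Section 2.1.3 attaches no hypothesis test to endpoint 3. This is correct.

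A reader might go further and infer that these deaths escape the CEC, so that a fatal event labelled by the site as generator failure could never be reassigned to the DF4 header or the Protego lead, and a primary event would be missed. The documents do not support this. Sections 4.2 and 10.2 also give the CEC every reported AE, and the form required by Section 3.3.2 makes the death a reported AE. A lost primary event would further need mislabelling, no adjudication, and a relation the CEC would have judged definite, and nothing in the plan points to that chain. The two CEC sentences are inconsistent with each other; they do not show that these deaths are excluded.

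**Conclusion.** The point holds for RA and LV leads. A non-procedural AE that is fatal before any listed action is in neither endpoint under Section 10.3.2, contrary to the unconditional description of endpoint 3 in Sections 2.1.3, 2.4.1 and 10.2. For generator AEs other than the two header types, and for non-system AEs, the wording is ambiguous. CEC scope needs to be reconciled.

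The effect is limited to reported endpoint 3 rates and intervals: 0.1 percentage point per omitted death, assuming 1000 evaluable subjects and an unknown number of deaths. Loss from the denominator also assumes that Section 2.4.3 refers to AEs counted for the endpoint and that the subject has no other. Power, type I error and the primary endpoints are not shown to be affected. Severity is minor.

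**What to change.** 1. In Section 10.3.2, state that a death resulting from an RA or LV lead-related, pulse generator-related or non-procedure non-system-related AE counts in secondary endpoint 3 whether or not an intervention was performed, unless it is already counted in the primary endpoints.
2. In Section 10.1.4, extend the condition to events that require a revision or explant *or result in death*. Without this, a fatal secondary infection may not fall in the class at all, and the change to Section 10.3.2 would not reach it.
3. In Sections 4.2 and 10.2, reconcile the two statements of CEC scope so that these deaths are adjudicated. Section 2.1.3 makes adjudication part of the definition of endpoint 3, so this is needed for the first change to work.

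The cost is short edits in four sections, a few more adjudications by a committee that already exists, and possibly a slightly higher endpoint 3 rate. No new data collection is needed, because Section 3.3.2 already asks for the AE form and the device relation of each death.
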